8.2 Serious Adverse Events (SAEs)

A SAE is any untoward medical occurrence that

- led to death,
- Ied to serious deterioration in the health of the subject, that either resulted in
 - > a life-threatening illness or injury, or
 - > a permanent impairment of a body structure or a body function, or
 - > hospitalisation or prolongation of patient hospitalisation, or
 - medical or surgical intervention to prevent life-threatening illness or injury or permanent impairment to a body structure or a body function,
 - > a chronic disease,
- Ied to foetal distress, foetal death or a congenital abnormality or birth defect.

More than one of the above criteria can be applicable to each event.

These characteristics/consequences have to be considered at the time of the event. For example, regarding a life-threatening event, this refers to an event in which the subject was at risk of death at the time of the event. It does not refer to an event which hypothetically might have caused death if it were more severe.

NOTE:

The following overnight hospitalisations are not considered SAEs:

- Not urgent hospitalisation for
 - > a condition existing before signing consent, or
 - > a procedure required by the study protocol without serious deterioration in health.
- Elective inpatient hospitalisation (e.g. surgery) verifiably planned before signing consent.
- Any overnight hospital stay required only for diagnostic procedure (e.g. in a sleep laboratory).

8.3 Device Related Adverse Events

This study uses a diagnostic IP, only. Causal relationship of adverse events has to be assessed in relation to the IP, only. It will be assessed and reported by the sponsor.

However, classification of adverse events as related to other medical devices or therapies used within the trial will follow the definitions as given for routine clinical care. Treating physicians have to report adverse events related to other medical devices or therapies to the corresponding manufacturer of the device. Reporting duties of manufacturers of other than the IP device used within this diagnostic trial have to follow routine procedures relevant for marketed medical devices.

8.3.1 Adverse Device Effect (ADE)

An adverse event related to the use of an IP. This definition includes adverse events resulting from insufficient or inadequate instructions for use, deployment, implantation, installation, or operation, or any malfunction of the IP. It also includes any event resulting from use error or from intentional misuse of the IP.

8.3.2 Serious Adverse Device Effect (SADE)

An adverse device effect that has resulted in any of the consequences to the characteristic of a serious adverse event. According to EU MDR Article 80 any serious adverse event that has a causal relationship with

the IP, the comparator or the investigation procedure or where such causal relationship is reasonably possible will be reported without delay to all involved authorities.

8.3.3 Device Deficiency (DD)

Device deficiencies are defined as inadequacy of an IP with respect to its identity, quality, durability, reliability, safety or performance. Device deficiencies include malfunctions, use errors and inadequacy of information provided by the manufacturer, including labelling. All device deficiencies shall be documented and appropriately managed by the sponsor.

Device deficiencies that might have led to a serious adverse event if appropriate action had not been taken, intervention had not occurred, or circumstances had been less fortunate also have to be recorded in the e-CRF and reported without delay to all involved authorities.

8.4 Recording and Reporting of SAEs by investigators

The investigator should specify and report in the e-CRF the nature of the sign or symptom leading to the SAE, the date of onset of the sign or symptom, the date of resolution of the specific event (not of the underlying disease), the intensity, interventions performed (if any), the relationship to the IP or the index thyroid surgery itself, and the outcome.

Following the patient's written consent to participate in the study, all SAEs, whether related or unrelated to the IP or the index thyroid surgery itself, must be reported expeditiously by the investigator to the sponsor through the SAE section of the e-CRF within 24 hours of becoming aware of the event and will subsequently be assessed by the sponsor and reported to authorities involved. An SAE form within the e-CRF should be completed for any event where doubt exists regarding its status of seriousness. As a minimum, the investigator has to fill out the following items of the internet-based SAE form:

- > Type of event
- > Description
- Date of onset
- Criteria for seriousness
- > Causal relationship to study therapy.

As soon as further information regarding the event is available (e.g. discharge letter), the investigator should complete the documentation in the e-CRF and sign it electronically. Copies of the discharge letter, of all reports regarding examinations carried out and/or diagnostic findings should be digitally provided to the CRO. For laboratory results, the laboratory normal ranges should be included. All documents should be digitally provided to the CRO.

Follow-up of any **SAE that is fatal or life threatening** should be digitally provided immediately but no later than **within two additional calendar days of becoming aware of the event**.

Any SAE recording (initial report and follow-up information on e.g. changes of an ongoing SAE's intensity or relationship to the IP or outcome) is done through the SAE section of the e-CRF. An automated e-mail notification system within the e-trial management system will inform sponsor and CRO instantaneously, thus, no extra SAE form needs to be send but sponsor and CRO will receive an automated digital notification on the SAE at the same time of the data being documented or changes of relevant SAE data being made in the e-CRF.

8.4.1 Definition of Intensity

Be aware that intensity of an adverse event and its seriousness are independent definitions, e.g. an adverse event might be serious but mild in intensity or vice versa.

Intensity	Definition
Mild	Patient is aware of signs and symptoms but they are easily tolerated
Moderate	Signs/symptoms cause sufficient discomfort to interfere with usual activities
Severe	Patient is incapable to work or perform usual activities

8.4.2 Definition of Causality

The sponsor and the investigators will use the following definitions to assess the relationship of SAEs to the IP or the investigation procedure.

Not related:

Relationship to the device or procedures can be excluded when:

- the event has no temporal relationship with the use of the IP, or the procedures related to application of the IP;
- the SAE does not follow a known response pattern to the medical device (if the response pattern is previously known) and is biologically implausible;
- the discontinuation of medical device application or the reduction of the level of activation/exposure when clinically feasible - and reintroduction of its use (or increase of the level of activation/exposure), do not impact on the SAE;
- the event involves a body-site or an organ that cannot be affected by the device or procedure;
- the SAE can be attributed to another cause (e.g. an underlying or concurrent illness/ clinical condition, an
 effect of another device, drug, treatment or other risk factors);
- the event does not depend on a false result given by the IP used for diagnosis, when applicable;

In order to establish the non-relatedness, not all the criteria listed above might be met at the same time, depending on the type of device/procedures and the SAE.

Possible

The relationship with the use of the IP or the relationship with procedures, is weak but cannot be ruled out completely. Alternative causes are also possible (e.g. an underlying or concurrent illness/ clinical condition or/and an effect of another device, drug or treatment). Cases where relatedness cannot be assessed, or no information has been obtained should also be classified as possible.

Probable

The relationship with the use of the IP or the relationship with procedures, seems relevant and/or the event cannot be reasonably explained by another cause.

Causal relationship

The SAE is associated with the IP or with procedures beyond reasonable doubt when:

- the event is a known side effect of the product category the device belongs to or of similar devices and procedures;
- the event has a temporal relationship with IP use/application or procedures;
- the event involves a body-site or organ that
 - > the IP or procedures are applied to;
 - > the IP or procedures have an effect on;

- the SAE follows a known response pattern to the medical device (if the response pattern is previously known);
- the discontinuation of medical device application (or reduction of the level of activation/exposure) and reintroduction of its use (or increase of the level of activation/exposure), impact on the SAE (when clinically feasible);
- other possible causes (e.g. an underlying or concurrent illness/ clinical condition or/and an effect of another device, drug or treatment) have been adequately ruled out;
- harm to the subject is due to error in use;
- the event depends on a false result given by the IP used for diagnosis, when applicable;

In order to establish the relatedness, not all the criteria listed above might be met at the same time, depending on the type of device/procedures and the SAE.

The sponsor and the investigators will distinguish between the SAEs related to the IP and those related to the procedures (any procedure specific to the clinical investigation). If routine procedures are not imposed by the clinical investigation plan, complications caused by them are also considered not related.

8.5 Adverse Event Follow-up Procedures

The investigator should take all appropriate measures to ensure the safety of the patients and should therefore follow-up the outcome of any SAE (clinical signs, laboratory values etc.) until the return to normal or consolidation of the patient's condition. Thus, an SAE, i.e. the event primarily fulfilling criteria of seriousness, may end even if the underlying disease is still ongoing.

In case of any SAE, the patient must be followed until clinical recovery is completed and/or laboratory results have returned to normal, or until progression has been stabilised. This may imply that follow-up will continue after termination of the trial, and that additional investigation may be requested by the CRO. This may mean that the CRO will ask the investigator for further clinical reports and documents, even if these are generated after the end of the patient's participation in the trial, if this is needed to finally assess the outcome of a SAE and of the patient's safety with respect to this SAE.

8.6 Recording and Reporting of events to authorities

In general, AEs, SAEs and device deficiency will be assessed by the sponsor and reported to authorities involved.

Reportable events to authorities in accordance with EU MDR Article 80 are:

- a) any serious adverse event that has a causal relationship with the IP, the comparator or the investigation procedure or where such causal relationship is reasonably possible;
- b) any device deficiency that might have led to a serious adverse event if appropriate action had not been taken, intervention had not occurred, or circumstances had been less fortunate;
- c) any new findings in relation to any event referred to in points a) and b).

For all **reportable events which indicate an imminent risk** of death, serious injury, or serious illness and that requires prompt remedial action for other patients/subjects, users or other persons or a new finding to it, the sponsor will report to authorities immediately, but not later than **2 calendar days** after awareness by sponsor of a new reportable event or of new information in relation with an already reported event.

This includes events that are of significant and unexpected nature such that they become alerting as a potential public health hazard. It also includes the possibility of multiple deaths occurring at short intervals. Any other reportable events or a new finding/update to it, will be reported by the sponsor to involved authorities immediately, but not later than **7 calendar days** following the date of awareness by the sponsor of the new reportable event or of new information in relation with an already reported event.

The sponsor will report in line with EU guidelines (e.g. using SAE collection table of the MDCG guideline "Guidance on safety reporting in clinical investigations") and/or national guidelines (e.g. reporting forms of individual SAEs of the German BfArM), if applicable. The quarterly SAE summary will also be reported.

Routine clinical requirements for physicians of reporting deficiencies of non-IP devices or drug reactions to the corresponding manufacturer as defined in applicable regulatory documents for routine clinical care reporting are not touched by this procedural study definition.

9. Study Schedule

All data and assessments described in the following sections have to be documented as defined in the e-CRF, even if not described in detail in the study protocol.

9.1 Visit Schedule

The timing of study visits and assessments are outlined in Table 1. The term "visit" in the context of study procedures is related to both, clinical visits at the site as well as to documentation forms in the e-CRF.

Assessments and procedures	Baseline	1 month FU ^{1, 3}
Signed informed consent form	х	
Check of inclusion & exclusion criteria	х	
Medical history assessment	х	
Physical examination	х	
Clinical routine laboratory parameters ²	х	
Documentation of concomitant medication	х	
Thyroid surgery ⁵	х	
Generalised Anxiety Disorder questionnaire (GAD-7)	х	x
General Health Questionnaire (EQ-5D-5L)	х	x
Assessment of adverse events ⁴	х	x

Table 1: Study visit schedules and procedures

¹ Time window ± 7 days related to visit schedules as displayed in the e-CRF

² Blood sample not older than 2 weeks at the date of baseline visit

³ By means of patient questionnaires sent to and replied by the patient

⁴ Including provision of external medical documents

⁵ Within 3 months after patient's informed consent

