4.2 Secondary Endpoint Parameters

Secondary endpoint parameters are defined as:

- EP3. Safety of the use of the diagnostic IP by means of adverse events within 1 month following thyroid surgery.
- EP4. Sensitivity and specificity of the IP for detection of clinically relevant hemorrhage within 48 hours following thyroid surgery in a three-level decision system using 10 and 20 mmHg of pressure as cutoffs compared to detection in routine clinical care.
- EP5. Positive and negative predictive values of the IP for detection of clinically relevant hemorrhage within 48 hours following thyroid surgery using the two-level and the three-level decision system compared to detection in routine clinical care.

Clinically relevant hemorrhage and serious adverse events will be adjudicated by an independent Endpoint Review Committee (ERC) according to standardised definitions [7] given in the ERC charter. Outcome death in follow-up will be assessed as equivalent endpoint to clinically relevant hemorrhage.

Parameters relevant for endpoints within the test treatment study (stage 2) are collected within HEDOS study (diagnostic accuracy study, stage 1), too, e.g. clinical symptoms triggering surgical intervention of a suspected post-operative hemorrhage detected in routine clinical care, time to clinical or technical alerts, surgical interventions which did not show post-operative hemorrhage needing intervention.

5. Study Design

In general, the development of a diagnostic test is structured in four phases [1]. In phase I, the functionality and safety of the diagnostic test is examined. In phase II, the diagnostic test is applied to individuals with known disease status to define the cut-off value. Phase III evaluates the diagnostic accuracy based on the pre-defined cut-off value in patients with unknown disease status. Phase IV aims to determine patients' benefit of the test-treatment combination. Hence, the last two phases of the development process are combined. Two single studies are planned to be combined into a phase III/IV seamless design in which a confirmatory phase III diagnostic accuracy study (stage 1) and a subsequent phase IV cluster randomised test treatment study (stage 2) are connected to each other and data from the diagnostic accuracy study will also be used for the randomized test treatment study.

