8.1 Adverse Events (AEs)

Is any untoward medical occurrence, unintended disease or injury, or untoward clinical signs (including abnormal laboratory findings) in subjects, users or other persons, in the context of a clinical investigation whether or not related to the IP. This definition includes events that are anticipated as well as unanticipated events and those occurring in the context of a clinical investigation related to the IP or the procedures involved. For users or other persons, this definition is restricted to events related to IPs.

Any surgery procedure or other intervention irrespective of its relation to the IP or the index thyroid surgery is an AE and has to be documented.

A newly diagnosed concomitant disease is also considered an AE.

All AEs occurring from enrolment until end of follow-up of each study patient will be documented by study site personnel in the e-CRF immediately after study site personnel's awareness of the event, and will subsequently be assessed by the sponsor and reported to authorities involved.

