9.3 Follow-up

The day of index thyroid surgery is day 1 of follow-up on primary and secondary endpoints.

Each patient will be followed until one month after day of index thyroid surgery (\pm 7 days related to visit schedules as displayed in the e-CRF) or until withdrawal of consent (WOC) or death.

9.3.1 Clinical follow-up after 1 month using patient questionnaires

One month after day of index thyroid surgery (± 7 days related to visit schedules as displayed in the e-CRF) or triggered by documentation of withdrawal of consent (WOC), three questionnaires will be sent to the patients by their corresponding study sites together with toll-free envelopes for reply. Patients will be asked to:

- Complete the EQ-5D-5L and the GAD-7 questionnaires
- Document clinical events in a FU questionnaire which are suspicious as AEs.

In case of missing reply after one written reminder by the study site, the patient will be contacted by the study site by phone in order to obtain the required information.

In case a patient reports a clinical event, which is suspicious as SAE, the responsible study site will contact the patient's family doctor, and / or the hospital where the patient was treated, and ask for supporting documents (i.e. hospital discharge letter, diagnostic reports) as applicable. The study site is responsible for completion of the reported event data in the e-CRF.

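### The single post-discharge adverse-event questionnaire may go out up to 7 days before the EP3 month is over, and nothing later covers the missing days

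*Protocol*

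**What the plan says.** Section 4.2 defines EP3 as "Safety of the use of the diagnostic IP by means of adverse events within 1 month following thyroid surgery". It states no tolerance and does not give the month in days.

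Section 8.1 limits collection to the follow-up period: "All AEs occurring from enrolment until end of follow-up of each study patient will be documented". Section 9.3 sets the end of that period: "Each patient will be followed until one month after day of index thyroid surgery", and the same sentence carries a tolerance of 7 days either way. Sections 10.2 and 11.2 describe the duration as about one month.

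The one-month contact in Table 1 (9.1) has two relevant footnotes. Footnote 1 reads "Time window ± 7 days related to visit schedules as displayed in the e-CRF". Footnote 3 gives the mode: "By means of patient questionnaires sent to and replied by the patient". Section 9.3.1 says that at one month, with the same tolerance, "three questionnaires will be sent to the patients by their corresponding study sites together with toll-free envelopes for reply". It adds: "In case of missing reply after one written reminder by the study site, the patient will be contacted by the study site by phone".

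The follow-up form in Appendix III asks about hospital stays, doctor visits, new chronic disease and complaints since discharge. It asks for calendar dates of stays, visits and onset of complaints, and its header asks for the date of completion. It sets no end date for the recall period. Section 12.1.3 makes the safety analysis descriptive.

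**The concern.** EP3 is cumulative: it counts events over a period with a fixed end. A tolerance on both sides suits a point measurement such as a quality-of-life score, where a week either way changes little. For a cumulative count, the negative side removes days from the period being reported.

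The form looks back from its completion to discharge, so it cannot ask about days still to come. The reminder and the phone call apply only when no reply arrives. A patient who replies promptly to an early mailing therefore has no later scheduled enquiry, although the whole process complies with the protocol.

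At stake is the completeness of the stated safety endpoint for a device without market approval. The error has one direction, because days not asked about can only lower the number of events found. It arises in data collection, so no rule in the statistical analysis plan can repair it.

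**Working it through.** The protocol states no figure on this point, so there is none to reproduce. The check is day arithmetic.

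**Inputs**
- EP3 period: 1 month (4.2). The protocol does not give it in days, so 30 days is assumed, with a range of 28 to 31.
- Tolerance: 7 days either way (Table 1 footnote 1; 9.3; 9.3.1).
- Planned patients: 1,470 (12.2), used only for scale.
- Distribution of sending dates: not given. An even spread over the window is assumed.
- Delay from sending to completion: not given. Values of 0, 3, 5 and 7 days are assumed.

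**Extreme case for one patient**
- Form sent at the early edge and completed the same day: 30 − 7 = day 23 (range 28 − 7 = 21 to 31 − 7 = 24).
- Share of the EP3 month not asked about: 7/30 = 23.3% (range 7/31 = 22.6% to 7/28 = 25.0%).
- If this happened to all 1,470 patients: 1,470 × 7 = 10,290 of 1,470 × 30 = 44,100 patient-days.
- If 10%, 25% or 50% of patients were closed at −7 days: 2.3%, 5.8% or 11.7% of patient-days.

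**Average loss with no reply delay**
- Continuous even spread from −7 to +7: half the patients are early and lose 3.5 days on average, so 0.5 × 3.5 = 1.75 days, and 1.75/30 = 5.8%.
- Whole days from −7 to +7 (15 values): 28/15 = 1.87 days, and 1.87/30 = 6.2%, with 7/15 = 47% of patients contacted early.
- Both give about 6%.

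**Average loss with a reply delay of d days**

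Completion then runs from −7 + d to +7 + d. The mean loss over the continuous spread is (7 − d)²/(2 × 14).
- d = 3: 16/28 = 0.57 days, 1.9% of the month.
- d = 5: 4/28 = 0.14 days, 0.5%.
- d = 7: 0 days.

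**The late side**

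A form completed after one month can report later events. EP3 is restricted to the month and the form asks for dates, so such events can be removed. The late edge adds nothing to EP3.

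All of these are patient-days, not events. The protocol gives no adverse-event rate for the fourth week.

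**The case against.** The strongest reply is that this is a conventional visit window and that its practical effect is small.

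- The tolerance is openly stated in 9.3 itself, and the follow-up duration is called approximate in 10.2 and 11.2. A reader might infer a contradiction between 4.2 and 9.3, but the month is nominal throughout. This part of the reply stands: the point is a loose fit between endpoint and contact, not a contradiction.
- In 9.3.1 the window governs sending. Postal time, the reminder and the phone call all move completion later. This stands, and it is why the average loss is about 0 to 2% under the assumed delays.
- A reader might infer that short observation cannot be told apart from event-free observation. The completion date on the form rules that out, since each patient's recall end is recorded. The date identifies the gap but does not fill it.
- A reader might infer that EP3 mixes patients observed for 23 days with patients observed for 37. With EP3 limited to the month and events dated, the upper end is capped at 30 days.
- A reader might infer that device-related infection is under-counted. The sensor is removed at about 48 hours (3.3.1, 7.1), and nothing in the protocol indicates such infections arising in the fourth week.
- Serious events must be reported within 24 hours of the site becoming aware of them (8.4), whatever the questionnaire shows. This helps only if the site learns of the event without asking.
- EP3 is secondary and descriptive. The co-primary accuracy endpoints concern the first 48 hours and are untouched.

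What the reply does not answer is the patient who completes the form before the month ends. For that patient no later contact is scheduled.

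**Conclusion.** The point holds as a minor one. The protocol allows the only scheduled post-discharge adverse-event enquiry, and with it follow-up, to fall up to 7 days before the EP3 month is complete. A patient who has replied is not contacted again. The loss is 7 of 30 days (23%) at the extreme. Averaged over patients it is about 6% of the month with no reply delay and about 0 to 2% with a delay of 3 to 7 days. These averages assume a 30-day month and evenly spread sending dates. They would be larger if sites routinely sent early, and the 23% would apply to the whole trial only if every form were sent at −7 days and answered the same day.

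The effect can only lower the adverse-event count. The documents do not allow it to be expressed as a number of missed events. Sample size, power, type I error and the accuracy endpoints are unaffected.

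**What to change.** - In Table 1, 9.3 and 9.3.1, remove the negative tolerance for the one-month adverse-event questionnaire, for example 0/+7 days.
- Define one month in days, counted from the day of surgery.
- State that EP3 counts events by onset date within that period, using the dates the form already asks for.
- Where a form is nevertheless completed before the period ends, have the site cover the remaining days by phone, extending the call that 9.3.1 already provides for missing replies.

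For every patient who replies or is reached by phone, the unasked part of the EP3 month then falls to 0 days.

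The cost is protocol and e-CRF wording, plus a phone call for each early form. Last patient last visit may move by about a week. The EQ-5D-5L and GAD-7 travel in the same mailing and shift slightly later. With 0/+7 days they are still sent within the present window, and under an even spread the mean sending time moves from 0 to +3.5 days. No patients or procedures are added.
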